## 1 BACKGROUND INFORMATION AND RATIONALE

### 1.1 Introduction

The incidence of dislocation following total hip arthroplasty (THA) has been reported to be from 1 percent to as much as 3.2 percent (Woo and Morrey 1982; Pellicci 1998). The demand for THA is expected to increase. Post dislocation solutions include closed reduction, open reduction, THA revision and constrained cup, conversion to hemi-arthroplasty, allograft, or girdlestone resection. These solutions are often costly, painful, and can involve substantial additional risks and complications. Acetabular cup placement is an important factor in the stability of the THA. Cup malpositioning has been associated with bearing surface wear and dislocation (Callanan, 2011). For most subjects, acceptable angles are 40 degrees of abduction ( $\pm 10$  degrees) and 20 degrees ( $\pm 5$  degrees) of version (Lewinnek 1978; Soong 2004). However, malpositioning continues to occur resulting in cup angles outside acceptable ranges which leaves subjects with an increased risk of dislocation.

### 1.2 Name and Description of Investigational Product or Intervention

This study will involve a quantitative assessment of prospectively collected computed tomography, radiographic, and patient reported outcomes data from multiple centers.

### 1.3 Compliance Statement

This study will be conducted in full accordance with all applicable West Virginia University Research Policies and Procedures and all applicable federal and state laws and regulations including 45 CFR and 46. All episodes of noncompliance will be documented.

The investigators will perform the study in accordance with this protocol, will obtain consent and assent (if applicable), and will report unanticipated problems involving risks to subjects or others in accordance with the WVU Institutional Review Board (IRB) Policies and Procedures and all federal requirements. Collection, recording, and reporting of data will be accurate and will ensure the privacy, health, and welfare of research subjects during and after the study.

## 2 STUDY OBJECTIVES

### 2.1 Primary Objective (or Aim)

The objective of this study is to examine the acetabular cup placement of THA subjects and compare results for subjects who undergo THA with robotic-arm assistance to those who undergo traditional THA. The central hypothesis is that robotic-arm assisted acetabular cups will have greater accuracy of placement and better long-term outcomes over those traditionally placed. To obtain the most definitive assessment of cup placement, the study will utilize a digital imaging analysis program called the Martell Hip Analysis Suite (HAS, Chicago, IL) as well as computed tomography (CT) scans. Patient reported outcomes (HOOS, PROMIS10, hip stability, and return to function) will also be collected at specified intervals. Using CT scans and HAS analysis allows for a complete description of cup

placement and better accounts for factors such as pelvic rotation and/or tilt, otherwise not accounted for in radiographic analysis (Ghelman 2009).

## **2.2 Secondary Objectives (or Aim)**

**Specific Aim #1:** Determine the accuracy of placement of robotic-arm assisted acetabular cups versus manual cup placement. The working hypothesis is that robotic-arm assisted cup placement will demonstrate more accurate cup placement compared to conventional manual cup placement.

**Specific Aim #2:** Assess the frequency with which the robotic-arm assisted placements of acetabular cups are accurately placed compared to the surgical plan. The working hypothesis is that robotic-arm assisted THA will demonstrate greater accuracy by adhering to the surgical plan more frequently than non-robotic-arm assisted cases.

**Specific Aim #3:** Examine the patient reported outcomes of robotic-arm assisted THA subjects. The working hypothesis is that subjects undergoing robotic-arm assisted acetabular cup placement will report better outcomes than subjects with conventional manual cup placements.

## **3 INVESTIGATIONAL PLAN**

### **3.1 General Schema of Study Design**

Subjects of eight surgeons at two institutions (Allegheny Health Network or AHN and West Virginia University or WVU) will be enrolled in the study, providing a valuable multi-center perspective and reducing the inherent bias produced from a single surgeon or single site study. This group of providers represents surgeons at varying levels of experience which are average annual volume, and robotic experience, factors found to contribute to accuracy of cup placement (Callanan 2010). Our institution will conduct this study at WVU Medicine and at two sites that are part of AHN, Allegheny General Hospital (AGH) and Forbes Regional Hospital. We will enroll a total of 192 subjects, which is 24 subjects per surgeon.

### **3.2 Allocation to Treatment Groups and Blinding**

### **3.3 Duration of Study Participation**

The study duration per subject will be up to 2 years ( $\pm 6$  months).

### **3.4 Total Number of Study Sites/Total Number of Subjects Projected**

To achieve accuracy of cup placement within 5 degrees of the target version (40 degrees  $\pm 5$ ) and abduction (20 degrees  $\pm 5$ ) angles 90 percent of the time, we will enroll 24 subjects per provider. The study will be conducted at two investigative sites in the United States and recruitment will stop when a total of 192 subjects are enrolled at these facilities. It is expected that 120 subjects will be enrolled at WVU Medicine, 48 subjects will be enrolled at Allegheny General Hospital (AGH), and 24 subjects at Forbes Regional Hospital.

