## 6 STATISTICAL CONSIDERATIONS

### 6.1 Sample Size and Power

Patient characteristics and demographics will be analyzed using Chi-square or Fisher's exact test as appropriate for categorical variables and parametric and non-parametric hypotheses tests for continuous variables as appropriate. The central hypothesis will be evaluated using a univariate logistic regression model to determine the accuracy of cup placement using the NON-ROBOTIC ARM group as the reference. Confounding factors will be controlled for in the model and interaction between terms will also be evaluated.

Data will be analyzed by the West Virginia University biostatistics team/core; other tests may be added at the discretion of those experts.

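### Section 3.4 swaps the labels in the trial's only numeric cup-accuracy target: version is set at 40 degrees and abduction at 20, the reverse of Section 1.1

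*Combined protocol and SAP*

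**What the plan says.** Section 3.4 of the combined protocol and SAP justifies enrolment by an accuracy goal. Cups are to be placed "within 5 degrees of the target version (40 degrees", with a tolerance of ±5, and at an abduction of 20 degrees, also ±5. The same sentence adds a success rate and links it to recruitment: "angles 90 percent of the time, we will enroll 24 subjects per provider".

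Section 1.1 states the ranges regarded as acceptable for most subjects, citing published sources: "acceptable angles are 40 degrees of abduction", with a tolerance of ±10, and 20 degrees of version, with a tolerance of ±5. It then motivates the trial by noting that "malpositioning continues to occur resulting in cup angles outside acceptable ranges".

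No other section gives a cup angle in degrees. In Section 2.2, Aim 1 compares accuracy without a number, and Aim 2 asks how often "acetabular cups are accurately placed compared to the surgical plan", without a tolerance. Section 6.1 names a "univariate logistic regression model to determine the accuracy of cup placement" but gives no cut-off and refers to neither Section 1.1 nor Section 3.4.

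**The concern.** The two sections pair the same two central values, 40 and 20 degrees, with opposite angles. If Section 1.1 describes an acceptable cup, Section 3.4 sets a target that such a cup cannot meet. If Section 3.4 is taken literally, every cup that Section 1.1 calls acceptable is a miss.

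The location gives the slip its weight. Section 1.1 is background. Section 3.4 is where the trial sets its own goal, with an angle window, a required rate of 90 percent and a link to the number enrolled. Nothing later restates or corrects the angles. What is at stake is a wrong threshold standing in the protocol as the trial's stated numeric goal.

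**Working it through.** **The plan's own counts.** Section 3.1 has eight surgeons with 24 subjects each: 8 × 24 = 192. Section 3.4 splits these by site: 120 + 48 + 24 = 192. Both agree with the stated total. The 24 per surgeon cannot be rederived, because the documents give no alpha, power or control-arm rate. No angle enters any stated calculation, so the labels do not affect these counts.

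**Inputs.** Each window is centre ± tolerance.

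| Angle | Section 1.1 | Section 3.4 as written | Section 3.4, labels exchanged |
|---|---|---|---|
| Abduction | 40 ± 10 = 30–50 | 20 ± 5 = 15–25 | 40 ± 5 = 35–45 |
| Version | 20 ± 5 = 15–25 | 40 ± 5 = 35–45 | 20 ± 5 = 15–25 |

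**As written.**
- Distance between centres: abduction |40 − 20| = 20 degrees; version |20 − 40| = 20 degrees.
- Gap between windows (lower limit of the higher window minus upper limit of the lower one): abduction 30 − 25 = 5 degrees; version 35 − 25 = 10 degrees.
- Both gaps are positive, so the overlap is 0 on each angle. A cup at the exact Section 1.1 centre (abduction 40, version 20) fails Section 3.4 on both angles.

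**A more generous reading.** Suppose the 5-degree allowance is added on top of the ±5. Version becomes 40 ± 10 = 30–50, still 30 − 25 = 5 degrees clear of 15–25. Abduction becomes 20 ± 10 = 10–30, which touches 30–50 only at 30. Because the version windows remain disjoint, still no cup satisfies both sections.

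**With the labels exchanged.** The centre differences are |40 − 40| = 0 and |20 − 20| = 0. The version windows are identical (15–25). The abduction window 35–45 lies wholly inside 30–50 and is half as wide (10 of 20 degrees). One exchange therefore removes the whole contradiction and leaves only a narrower tolerance on abduction.

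**The case against.** The strongest reply is that this is a recognisable typing error with little consequence. The other pairing is already in Section 1.1, and an analyst would probably notice. The sample size does not move. Nothing in the documents says that surgeons, image readers or the robotic system take their targets from Section 3.4, and Aim 2 is judged against the surgical plan. Section 3.4 is also a rationale for enrolment, under a heading about sites and subject numbers, and is not presented as an endpoint definition.

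Most of that stands, and it limits how far the point goes. It does not remove the point. The sentence is intact running prose, it is wrong as written, no later text corrects it, and it holds the only numeric angle target the trial sets for itself.

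A reader might infer three stronger things that the documents do not support:
- **That the swapped window scores the logistic outcome, so the main analysis would be miscoded.** Section 6.1 does not say which window, if any, defines accuracy. That missing cut-off would exist even if Section 3.4 were correctly labelled. It is a separate matter.
- **That ±5 on abduction in Section 3.4 conflicts with ±10 in Section 1.1.** A study target can be deliberately tighter than a background acceptable range, and the two can coexist.
- **That the arithmetic of the sample size is wrong.** It is not; the counts agree.

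**Conclusion.** The point holds as a labelling error in Section 3.4. As written, its centres differ from those of Section 1.1 by 20 degrees on each angle. The windows are separated by 5 degrees on abduction and 10 degrees on version, and no cup can satisfy both sections.

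The contradiction needs no assumption about how cup angles are distributed. The direction of the correction rests on one: that Section 1.1 has the intended pairing. The support for this is that Section 1.1 attributes its ranges to published sources, whereas Section 3.4 cites none. Those sources were not available for checking, but the sponsor can confirm the pairing at once.

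The finding is that a stated threshold is wrong. It predicts nothing about the trial's results and makes no claim about power or about how Section 6.1 will be coded.

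**What to change.** Correct the sentence in Section 3.4 so that the target reads abduction 40 degrees ±5 and version 20 degrees ±5, met 90 percent of the time. Keep ±5 on abduction if the tighter target is intended; the correction does not require changing it.

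The cost is a wording change to one sentence. No visit, scan or measurement is added, and enrolment stays at 24 per surgeon and 192 in total.

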## **8.8 Recruitment Strategy**

The orthopaedic surgeon investigators will screen viable subjects from their pre-operative orthopaedic surgery clinic. If agreeable, subjects will consent and enroll in the study at this visit. Advertising will not be used. There will be sufficient subjects to achieve enrollment goals within the practice.

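### The only sample-size rationale (24 per provider, to achieve 90% accurate placement) does not follow, cannot be derived from any stated input, and does not match the comparison in Section 6.1

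*Combined protocol and SAP*

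**What the plan says.** Section 3.4 opens with an accuracy goal, "To achieve accuracy of cup placement within 5 degrees of the target version" and abduction, and gives the number enrolled as the means of meeting it: "angles 90 percent of the time, we will enroll 24 subjects per provider". It then says "recruitment will stop when a total of 192 subjects are enrolled at these facilities" and expects "120 subjects will be enrolled at WVU Medicine, 48 subjects will be enrolled at Allegheny General Hospital (AGH), and 24 subjects at Forbes Regional Hospital". Section 3.1 repeats the number without a reason: "We will enroll a total of 192 subjects, which is 24 subjects per surgeon".

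Section 6.1 is headed Sample Size and Power but contains neither. It describes the analysis: "The central hypothesis will be evaluated using a univariate logistic regression model to determine the accuracy of cup placement", with the non-robotic group as reference, control for confounders and evaluation of interactions. Section 8.1 randomises patients between robotic and traditional surgery from a schedule prepared in advance, and no allocation ratio is stated. Under Section 8.8, "subjects will consent and enroll in the study at this visit", that is, at the pre-operative clinic. In the Section 4 schedule, the first post-operative CT and Martell hip analysis fall at 3–6 months.

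**The concern.** The sentence gives the design a property that no number of patients can confer. Accuracy belongs to the technique and the surgeon; the number enrolled only determines how precisely accuracy is estimated, or how likely a difference is to be detected. Section 3.4 also speaks of a per-provider benchmark, while the objectives in Section 2 and the model in Section 6.1 are comparative.

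Two things are at stake. A reader could take the trial as sized to establish 90% accuracy for each surgeon. And the comparison the trial is there to make has no stated detectable difference, so a null result could not be judged against what the trial was able to find.

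**Working it through.** **1. The plan's own sums.** 8 surgeons × 24 = 192, and 120 + 48 + 24 = 192. Both check.

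**2. Can 24 be derived?** Not from stated inputs: the documents give no alpha, power, control rate, SD, precision or loss rate. It appears only if one is supplied, for example:
- Precision: estimating 90% to within ±12 points at 95% confidence gives n = 1.96² × 0.9 × 0.1 / 0.12² = 24.01.
- Single-arm test of 90% against 65%: requiring at least 20 of 24 gives exact one-sided alpha 0.042 and power 0.915.
- 90% power for a 5-degree mean difference, two-sided 5%: n per arm = 2 × (1.96 + 1.2816)² × SD² / 5², which is 24 if SD is about 5.34 degrees. That would be 24 per arm, not per provider.

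The ±12 points, the 65% and the SD are not in the documents.

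**3. Could 24 show at least 90% for one provider?** Alpha is assumed to be one-sided 5% or 2.5%. With no misplaced cup, the exact lower limit is α^(1/n).

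| Result | One-sided 95% limit | Two-sided 95% limit |
|---|---|---|
| 24/24 | 0.05^(1/24) = 88.3% | 0.025^(1/24) = 85.8% |
| 12/12 (one arm, if 1:1) | 0.05^(1/12) = 77.9% | 0.025^(1/12) = 73.5% |

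Equivalently, if the true rate is 90%, 24/24 has probability 0.9²⁴ = 0.080, so no result in 24 rejects a rate of 90% or less at one-sided 5%. The smallest zero-failure n that would is ln(0.05)/ln(0.9) = 28.4, so 29, or ln(0.025)/ln(0.9) = 35.01, so 36. An observed 22/24 (91.7%) has an exact 95% interval of 73.0% to 99.0%.

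**4. What does 192 deliver between arms?** Assumptions: 1:1 allocation (96 per arm), two-sided 5%, robotic rate 90%, no surgeon clustering. Power is the sum of the two binomial probabilities over all outcome pairs that reject.

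| Manual rate | Chi-square, 96 v 96 | Fisher, 96 v 96 | Chi-square, 86 v 86 |
|---|---|---|---|
| 75% | 79.7% | about 74% | about 75% |
| 80% | 49.8% | about 42% | about 45% |

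The 86 per arm assumes that 10% lack a reading (96 × 0.9 = 86.4).

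Normal-approximation check, Φ{[√n × Δ − 1.96√(2p̄q̄)] / √(p₁q₁ + p₂q₂)}:
- 90% v 75%: (1.470 − 1.053)/0.527 = 0.79, power 78.5%.
- 90% v 80%: (0.980 − 0.990)/0.5 = −0.02, power 49.2%.

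**The case against.** The sentence can be read as loose shorthand for a calculation that was not written down. On that reading the fault is missing inputs, not a wrong step, and the ±12-point result shows that 24 could have come from a precision aim. This stands in part: 24 is underivable, not shown to be wrong. It does not rescue the sentence, because no such aim is stated and a precision aim is still not a way to achieve accuracy.

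The failure in step 3 also depends on alpha, which the plan does not give. At one-sided 10%, 24/24 would pass (0.1^(1/24) = 90.9%), but only with both methods counted together and no failure.

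A reader might infer several stronger things that the documents do not support:
- *That the trial is too small, or 192 is wrong.* Without a stated control rate or target difference, this cannot be shown.
- *That 90% accuracy cannot be demonstrated at all.* The limit in step 3 is per provider. With 96 robotic cases, 93/96 or more would exclude 90% at one-sided 2.5%, with probability 0.29 if the true rate is 95% and 0.87 if it is 98%.
- *That Section 6.1 ignores surgeon.* It neither names surgeon nor excludes a surgeon term or interaction.
- *That fewer than 24 per provider will certainly be measured.* Counting at consent makes loss likely, but no rate is given; the 10% is illustrative.
- *That per-surgeon claims are planned, or that 90% is a formal threshold.* No per-surgeon analysis is described, and the aims are comparative.

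**Conclusion.** The concern holds as a fault in the rationale. The one sentence linking sample size to a goal claims something enrolment cannot do, rests on no stated input, and addresses a question other than the one analysed. On the reading that each provider should be shown to reach 90%, 24 falls short even with perfect results (88.3% one-sided, 85.8% two-sided), provided alpha is one-sided 5% or less; for one method at 1:1, the two-sided limit is 73.5%.

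For the comparison in Section 6.1, 192 gives roughly 74–80% power for 90% v 75% and 42–50% for 90% v 80%, depending on the test. Those figures rest on assumed 1:1 allocation, assumed rates, two-sided 5%, complete readings and no clustering. They describe what 192 can do under those assumptions; they do not reconstruct how it was chosen or judge whether it is enough.

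**What to change.** Delete the rationale in Section 3.4 that ties 24 per provider to reaching 90% accuracy. In 3.4 and 6.1, state what 192 delivers for the between-arm comparison, labelling each input as an assumption. For example:

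> Assuming 1:1 allocation (96 per arm), two-sided 5%, a robotic rate of 90% and no surgeon clustering, power is about 80% against a manual rate of 75% and about 50% against 80% (chi-square; about 74% and 42% with Fisher's exact test). If 10% lack a reading, power is about 75% and 45% (chi-square).

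If the sponsor holds an underlying calculation, state that instead, with its endpoint, control rate, alpha, power, allocation, and allowance for clustering and loss.

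Report percent accurate per arm with an exact 95% interval and the risk difference. Treat the 90% figure and any per-surgeon results as descriptive.

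When rewriting the sentence, reconcile its angle labels with Section 1.1: Section 3.4 attaches 40 degrees to version and 20 to abduction, while Section 1.1 has them the other way round. The accuracy endpoint cannot be applied until the two agree.

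The cost is protocol wording, with no more patients and no change of test. The stated capability becomes less favourable than the present sentence suggests.

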### **3.5 Study Population**

The study population is defined in section 3.6 (inclusion criteria) and 3.7 (exclusion criteria).

### **3.6 Inclusion Criteria**

- 1) Males and females age 18 years and older.
- 2) Subjects requiring primary total hip arthroplasty.
- 3) Subjects agreeable to randomization.
- 4) Subjects willing and able to comply with follow-up requirements.
- 5) Subjects willing to sign an IRB approved Informed Consent Form (ICF).

### **3.7 Exclusion Criteria**

- 1) Subjects with a Body Mass Index (BMI) >40.
- 2) Subjects with an active infection or suspected latent infection in or about the hip joint.
- 3) Bone stock that is inadequate for support or fixation of the prosthesis.
- 4) Previous major hip surgery excluding hip arthroscopy.
- 5) Total hip arthroplasty using cement fixation or resurfacing.
- 6) Pregnant or planning on becoming pregnant within the next two years.

Subjects that do not meet all of the enrollment criteria may not be enrolled. Any violations of these criteria must be reported in accordance with IRB Policies and Procedures.

## 4 STUDY PROCEDURES

	Screening/Pre-Op (-30 days)	Visit 2/Intra-op	Visit 3/3-6 months (± 1 months)	Visit 4/1 year (+ 3 months)	Visit 5/2 year (+ 6 months)
Consent	X				
Inclusion/Exclusion	X				
Demographics	X				
Medical History	X				
Surgical Details		X			
Function Evaluation/ROM	X		X	X	
HOOS	X		X	X	X
PROMIS 10	X		X	X	X
Dislocation/Ad Events			X	X	X
Radiographs	X		X	X	X
Computed Tomography	X		X		
HAS Analysis			X	X	X
Con Meds	X	X	X	X	X
Physical Exam	X				

### 4.1 Concomitant Medication

All prior and concomitant medications used within 30 days prior to the screening visit and through the end of the study will be recorded. The dates of administration, dosage, and reason for use will be included.

### 4.2 Subject Completion/Withdrawal

Subjects may withdraw from the study at any time without prejudice to their care. They may also be discontinued from the study at the discretion of the Investigator for lack of adherence to study treatment or visit schedules or adverse events (AEs). The Investigator may also withdraw subjects who violate the study plan, or to protect the subject for reasons of safety or for administrative reasons. It will be documented whether or not each subject completes the clinical study. If the Investigator becomes aware of any serious related adverse events, both serious and non-serious after the subject completes or withdraws from the study, they will be recorded in the source documents and on the case report form (CRF).

### 4.3 Early Termination Study Visit

Subjects who withdraw from the study will have all procedures enumerated for Visit 5 as the early termination visit.

## 5 STUDY EVALUATIONS AND MEASUREMENTS

### 5.1 Medical Record Review

- The following variables will be abstracted from the subject's electronic medical record: Preoperative Diagnosis [avascular necrosis/fracture, osteoarthritis, congenital/development dysplasia, and other (tumors, inflammatory disease, or metabolic diagnosis)].

